9.2.2. Summaries of Duration of Adverse Events

The duration of serious AEs, serious AEs resulting in hospitalization, and AEs in the ‘respiratory, thoracic and mediastinal disorders’ body system will be summarized.

The duration of AEs will be summarized (n, mean, standard deviation, median, minimum, and maximum) for each system/organ class and preferred term within the system organ class. The total duration is the sum of the duration for all AEs within a subject at the SOC level, for the SOC summaries and within the preferred term for preferred term summary. The maximum duration is the maximum of the durations for all AEs within a subject at the SOC level, for the SOC summaries, and within preferred term for the preferred term summary. The mean duration is the mean of the durations for all AEs within a subject at the SOC level, for the SOC summaries, and within preferred term for the preferred term summary.

The summary table of AE durations will also include a tabulation of the number of events per subject reported in the summary level (ie, SOC, preferred term level).

9.3. Total Duration and Compliance of ALIS Therapy

Duration and compliance summaries (ALIS only) will be presented by baseline to Month 6, Baseline to EOT, and Month 6 to EOT study periods. Duration of treatment and compliance will be summarized (n, mean, standard deviation, median, minimum, and maximum). Compliance will be categorized (>120%, 80-120%, <80%) and tabulated (number and percentage of subjects).

9.4. Concomitant and Other Medications

Concomitant medications will be coded using the WHO Drug Sept2016 dictionary. Tabulations will be done for the safety, populations. The number and percentage of subjects reporting the medication will be presented for subjects using at least 1 medication, at least one medication at the Anatomical Therapeutic Class Level 4 (ATC4) level, and by preferred term within ATC4.

9.5. Routine Laboratory Data

All clinical laboratory data summaries and tabulations will be based on the safety population.

At each visit, only those subjects providing data at the visit will appear on the tables.

The actual, baseline and change-from-baseline of the clinical laboratory results (blood chemistry and hematology) will be summarized (n, mean, standard deviation, median, minimum, and maximum) by visit for each prior treatment and total groups. At each visit the baseline summary will reflect those subjects who provided data at that visit.

Shifts-from-baseline-to-visit in categorization of result by normal ranges (low, normal, high, total) will be tabulated clinical laboratory results (blood chemistry and hematology) presenting the number and percentage of subjects in each cell. These shift tables will also be presented for clinically significant labs.

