#### 4.2 EXCLUSION CRITERIA

Subjects are not eligible to participate in the study if they meet any of the following criteria:

1. achieved culture conversion without relapse or recurrence in the INS-212 study by Month 6
2. early discontinuation (prior to Month 6 study visit) from INS-212
3. met any of the exclusion criteria of the INS-212 study, except for the following:
  - a. unable to perform the 6MWT
  - b. prior exposure to LAI (including clinical study)
  - c. in the opinion of the Investigator, patients who are not expected to survive the duration of the study
  - d. active allergic bronchopulmonary mycosis or any other condition requiring chronic systemic corticosteroids at a dose greater than the equivalent of 10 mg/day of prednisone within 3 months before Baseline (Day 1)
  - e. initiation of chronic therapy (e.g., high dose ibuprofen, inhaled anti-inflammatory agents including steroids, low dose maintenance steroids, rhDNase) at Baseline (Day 1)

Protocol Amendment 3.1: 25 May 2017

*This protocol is solely for communicating information about the investigational drug between Inmed Incorporated and study personnel. Information is not to be reproduced, abstracted or used for sharing of information for any other purpose, whatsoever, except with the written permission of Inmed Incorporated.*

4. positive pregnancy test or lactation. All women of child bearing potential will be tested. Women not of child bearing potential are defined as postmenopausal (i.e., amenorrheic for at least 1 year), or surgically or naturally sterile.
5. significant (as determined by the Investigator) hearing loss, vestibular dysfunction, or neuromuscular weakness where the potential risk of aminoglycoside toxicity outweighs the potential benefit
6. aspartate aminotransferase or alanine aminotransferase  $\geq 3$  times the upper limit of normal (ULN) and/or total bilirubin  $\geq 2$  times the ULN at their Month 6 study visit in INS-212
7. absolute neutrophil count  $\leq 500/\mu\text{L}$  at their Month 6 study visit in INS-212
8. serum creatinine  $>2$  times ULN at their Month 6 study visit in INS-212
9. current alcohol, medication abuse, or illicit drug abuse
10. any condition that, in the opinion of the Investigator, interferes with ability to safely complete the study or adhere to study requirements
11. diagnosis of myasthenia gravis

Protocol Amendment 3.1: 25 May 2017

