### 7.1.2 Clinical Laboratory Evaluations

The following clinical chemistry, hematology, and urine parameters comprise the clinical laboratory evaluations:

Clinical Chemistry	Sodium, chloride, potassium, bicarbonate (CO 2 ), magnesium, calcium, glucose, phosphate, total bilirubin (with direct and indirect fractionation, if total bilirubin is elevated >2 ULN), alkaline phosphatase, lactate dehydrogenase (LDH), aspartate aminotransferase (AST), alanine aminotransferase (ALT), albumin, total protein, creatinine, urea-nitrogen, uric acid, estimated glomerular filtration rate from the Cockcroft-Gault method
Hematology	Hemoglobin, erythrocytes, hematocrit, mean corpuscular hemoglobin (MCH), mean corpuscular volume (MCV), mean corpuscular hemoglobin concentration (MCHC), leukocytes, differential blood count of neutrophils, eosinophils, basophils, monocytes, lymphocytes, and platelets.
Urinalysis	Qualitative analysis of glucose, ketones, nitrites, protein, pH, leukocytes, blood, bilirubin, specific gravity; microscopic examination for cells, casts, and bacteria  Urine pregnancy test for women of child-bearing potential will be performed at the site and results will be entered into the eCRF.
Other Biomarkers	CRP and IL-6

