## 8.3 ADVERSE EVENTS OF SPECIAL INTEREST

Adverse events of special interest (AESI) are those known to be attributed to parenteral amikacin:

- nephrotoxicity, including elevation of serum creatinine, albuminuria, presence of red and white cells, casts, azotemia, and oliguria
- ototoxicity affecting the eighth cranial nerve resulting in hearing loss, loss of balance, or both.
- neuromuscular disorders
- allergic alveolitis
- bronchospasm
- hemoptysis

Cough is often associated with drug products that are nebulized. To properly characterize AEs of cough, specific details regarding AEs of cough will be reported in the AE eCRF pages.

It is expected that subjects in this study will experience a large number of pulmonary exacerbation events due to their underlying lung condition(s). Pulmonary exacerbation will be defined based on the Investigators best clinical judgment. Details of the type of exacerbation should be provided on the AE eCRF.

Protocol Amendment 3.1: 25 May 2017

*This protocol is solely for communicating information about the investigational drug between Inmed Incorporated and study personnel. Information is not to be reproduced, abstracted or used for sharing of information for any other purpose, whatsoever, except with the written permission of Inmed Incorporated.*

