13.3 Clinical Laboratory Evaluation

Laboratory parameters (hematology and chemistry) will be summarized using descriptive statistics at baseline and at each post-baseline time point. Changes from baseline will also be summarized. Baseline is defined as the last non-missing value prior to first dose of study drug in INS-312. Descriptive statistics at baseline and change from baseline is limited to continuous data. Laboratory parameters summary will be displayed by INS-212 treatment arm and overall.

Shift tables (ie, low-normal-high at baseline versus low-normal-high at follow-up in a 3-by-3 contingency table) will be provided to assess changes in laboratory values from baseline to each post-baseline visits. Reference ranges established by the central lab will be used to determine shifts. Determination of clinical significance for all out-of-range lab values will be made by the Investigator.

The numbers and percentages of subjects with clinically significant abnormal laboratory values will be summarized by each visit.

Clinical laboratory results will be provided in subject listings.

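### Measured creatinine is categorised only as low, normal or high at each visit, so the number of subjects with a large rise from their own Baseline is never counted

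*SAP*

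**What the plan says.** Final SAP 9.5 plans two displays of chemistry results. The first is continuous: "The actual, baseline and change-from-baseline of the clinical laboratory results (blood chemistry and hematology) will be summarized", by visit, with n, mean, SD, median, minimum and maximum, for each prior arm and in total. The second is categorical: "Shifts-from-baseline-to-visit in categorization of result by normal ranges (low, normal, high, total) will be tabulated clinical laboratory results". One sentence extends it: "These shift tables will also be presented for clinically significant labs". The final SAP does not say what makes a result clinically significant. The SAP for the initial analyses does, in its section 13.3: "Determination of clinical significance for all out-of-range lab values will be made by the Investigator". The final SAP's table list has only two chemistry tables, the by-visit summary (14.3.9.1.1) and the shift table (14.3.9.1.2).

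The renal analytes are in the chemistry panel of Protocol 7.1.2: "creatinine, urea-nitrogen, uric acid, estimated glomerular filtration rate from the Cockcroft-Gault method". Protocol 8.3 lists first among its adverse events of special interest (AESI) "nephrotoxicity, including elevation of serum creatinine, albuminuria, presence of red and white cells, casts, azotemia, and oliguria". At entry, Protocol 4.2 criterion 8 excludes serum creatinine more than 2 "times ULN at their Month 6 study visit in INS-212".

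Hearing is handled differently. Final SAP 6.4.8 defines grades from the threshold shift measured against the subject's baseline test, and 9.7 tabulates subjects by grade 0 to 4.

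**The concern.** A three-level scale tied to the reference range records only crossings of its limits. It does not record the size of a change that starts and ends in the same category. For creatinine this matters in two places: above ULN, where there is no further category to move into, and within the normal range, where a substantial relative rise may not reach ULN.

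Nephrotoxicity is a named aminoglycoside toxicity. AESIs and clinically significant laboratory abnormalities are both components of the primary endpoint. The study is open-label with no concurrent control, so a count taken from the measured values is the natural check on what investigators choose to report. As planned, a reader of the study report could not learn from any table how many subjects had, say, a 1.5-fold or twofold rise in creatinine.

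**Working it through.** The plan states no figure on this point, so there is nothing to reproduce. The check applies the 9.5 rule directly.

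**Inputs from the documents.** Categories low, normal and high (final SAP 9.5); entry limit of 2 x ULN at INS-212 Month 6 (Protocol 4.2); expected enrolment of about 200 (Protocol 3.6.1).

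**Inputs assumed.** The documents give no creatinine reference range, so LLN/ULN is varied from 0.40 to 0.65. They give no Baseline distribution either. INS-212's own exclusions, carried over by criterion 3, are not reproduced, so criterion 8 is taken as the operative limit. It applies at INS-212 Month 6, whereas Baseline is the later INS-212 EOT visit.

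**1. Baseline above ULN.** Baseline b > 1 (in ULN units) multiplied by any f ≥ 1 remains above 1.
- 1.05 x ULN, tripled: 1.05 × 3 = 3.15 x ULN, high-to-high.
- 1.5 x ULN, doubled: 1.5 × 2 = 3.0 x ULN, high-to-high.
- 2.0 x ULN, tripled: 2.0 × 3 = 6.0 x ULN, high-to-high.

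There is no upper bound, and this result needs no assumption about the reference range.

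**2. Baseline within the range.** The largest rise that stays normal-to-normal is ULN/LLN.

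| LLN/ULN | Largest unshifted rise | Doubling can be hidden? |
|---|---|---|
| 0.40 | 2.50-fold | yes |
| 0.45 | 2.22-fold | yes |
| 0.50 | 2.00-fold | only exactly at LLN |
| 0.55 | 1.82-fold | no |
| 0.60 | 1.67-fold | no |
| 0.65 | 1.54-fold | no |

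A 1.5-fold rise can therefore go unshifted at every ratio tried, for a Baseline between LLN and ULN/1.5. A doubling can do so only if ULN is at least 2 x LLN and Baseline is at or below ULN/2.

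**3. Share of subjects with that room (illustration).** The share is P(LLN ≤ Baseline ≤ ULN/f). Assume log-normal Baseline creatinine with mean 0.75 mg/dL and SD 0.20, and ULN 1.0 to 1.2 mg/dL.

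| LLN/ULN | f = 2 | f = 1.5 |
|---|---|---|
| 0.40 | 7% to 18% | 36% to 59% |
| 0.45 | 4% to 11% | 34% to 52% |
| 0.50 | 0% | 30% to 41% |
| 0.60 | 0% | 14% to 16% |

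These shares say who could rise that far without shifting. They do not say how many would.

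**4. Visibility in the change summary.** If k of N subjects double from 0.5 to 1.0 x ULN and the rest do not change, the mean change is k × 0.5/N.
- 1 of 200: 0.5/200 = 0.0025 x ULN.
- 10 of 200: 5/200 = 0.025 x ULN.

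The maximum is 0.5 x ULN in both cases, so it does not distinguish one affected subject from ten.

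**The case against.** A reader might infer from 9.5 that renal safety as a whole is judged only as low, normal or high. The documents do not support that. Final SAP Table 6 has a nephrotoxicity AESI group with terms for raised blood creatinine, reduced GFR, renal impairment and renal failure. AESIs are tabulated overall, by maximum toxicity grade, by relationship, and by withdrawal or interruption. The clinically significant shift tables use the terms of the primary endpoint.

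Nor can it be said that the plan hides every individual rise. The maximum change is printed at each visit, and chemistry values are listed by subject. eGFR is in the same panel. At fixed age and weight, Cockcroft-Gault eGFR halves when creatinine doubles, so an in-range doubling would appear in the eGFR change summary, and in its shift table if the laboratory supplies a range.

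It would also be wrong to present in-range doubling as generally possible: it disappears once LLN/ULN exceeds 0.50. The study is descriptive, and Protocol 9.6 asks for observed values, changes and shift tables, which the SAP broadly provides for chemistry.

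All of this stands, but it does not supply the missing count. Under Protocol 8.1 a laboratory finding becomes an adverse event through the Investigator's view of its relevance. In the initial SAP, the clinical-significance call covers out-of-range values, so an in-range rise falls outside it. The eGFR displays are again summary statistics and, at most, a normal-range shift. The listings would have to be counted by hand.

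**Conclusion.** The point holds as a gap in classification. No planned table counts subjects by the size of their measured creatinine rise, whereas hearing change is graded in this way.

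The high-to-high limb follows from the documents alone, although the share of subjects entering above ULN is unknown. The 1.5-fold limb holds for every range tried. The doubling limb is conditional on ULN being at least 2 x LLN. The percentage shares rest on an assumed distribution and range; they should be read as room for an unshifted rise, not as a forecast.

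No hypothesis test or sample size is affected. This is an inexpensive improvement to a component of the primary safety endpoint. It does not show that the planned renal reporting is void.

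**What to change.** In final SAP 9.5, add one table beside the existing shift table, overall and by prior INS-212 arm, giving the number and percentage of subjects by:
- the ratio of highest on-treatment creatinine to Baseline, in prespecified reporting categories (for example <1.5, 1.5 to <2, ≥2) or on the CTCAE v4.0 scale that Protocol 8.2.1 already uses for adverse events;
- the largest percentage fall from Baseline in the collected Cockcroft-Gault eGFR (for example ≥25%, ≥50%).

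State whether unscheduled results count towards the highest value, because final SAP 6.1 otherwise confines them to listings. The example cut-points are not taken from the documents. They are reporting categories only and imply no rule for managing subjects.

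The cost is one more table from data already collected. The reported renal signal may look slightly less favourable.

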9.6. Vital Signs

All vital signs data summaries and tabulations will be based on the safety population.

At each visit, only those subjects providing data at the visit will appear on the tables.

The actual, baseline and change-from-baseline of the vital signs will be summarized (n, mean, standard deviation, median, minimum, and maximum) by visit and timepoint (pre-dose and post-dose) for each prior treatment and overall. At each visit the baseline summary will reflect those subjects who provided data at that visit.

9.7. Audiology Tests

All audiology testing data summaries and tabulations will be based on the safety population.

At each visit, only those subjects providing data at the visit will appear on the tables.

The actual, baseline and change-from-baseline audiology test results at each will be summarized (n, mean, standard deviation, median, minimum, and maximum) by visit, frequency, and ear for each prior treatment and overall. At each visit the baseline summary will reflect those subjects who provided data at that visit.

The audiology results will be tabulated (number and percentage of subjects) by CTC grade (0, 1, 2, 3, 4) and total for either, left, and right ears within treatment and total groups.

9.8. Physical Examination

The site was instructed to report any changes found during the physical exam as AEs. There is no summary for physical examination.

11.2. Data Display Specifications

File formats

Unless otherwise specified, all outputs should be in RTF file format.

Page format

For submissions in the US, all outputs are presented in landscape orientation on 8.5x11 inch paper with Times New Roman or Courier New type face, 9-point font unless otherwise specified, and 1-inch margins on all sides.

For submissions in the EU, all outputs are presented in landscape orientation on A4 paper with Times New Roman or Courier New type face, 9-point font unless otherwise specified, and 2cm margins on all sides.

The hyphen (-) in table titles in the mock-ups indicates a line break.

Regions

Regions are, in order of appearance, 'All', 'North America', 'Japan', 'Europe', 'Oceania', and 'Asia (excluding Japan)'. When presenting data by region, there should be an 'All' group for each country and then the sites within that country should appear following the country. For categorical data, all categories should appear within each site.

Within each region the countries will be ordered by descending number of subjects enrolled to sites within that country. Similarly, within country the sites will be ordered by descending number of subjects enrolled to the sites.

On all tables by region, country, and site put a page break after each site.

Percentages

Unless otherwise indicated, percentages presented on a table will be based on the number of subjects in the column. Exceptions to this rule will be indicated in the footnote of those tables. If the count in a table is zero (0), only the count (0) should appear in the cell on the table (ie, no percentages or, in the case of AE tables, event counts). If there is a 100% there should be no decimal places presented (ie, 100% is 100).

Change-from-baseline Summaries

Tables of continuously valued parameters presenting change-from-baseline summaries will present, within each visit, 3 blocks of summary statistics for the observed cases (ie available data). The first block will present the 'actual', the second block will present, 'baseline' and the third block will present the 'change-from-baseline'. The 'actual' block will summarize the value collected at that visit. The 'baseline' block will summarize the baseline value for those subjects who have non-missing 'actual' values at the visit. The 'change-from-baseline' block will summarize the change-from-baseline value for subjects with non-missing 'actual' and 'baseline' values at the visit.

Mock-ups

Mock-ups of tables and listings are provided in separate documents.

11.3. Schedule of Events

INS-312	TREATMENT PHASE													OFF-ALIS TREATMENT PHASE
	Baseline	Month 1	Month 2 ^a	Month 3	Month 4 ^a	Month 5 ^a	Month 6	Month 7 ^a	Month 8 ^a	Month 9	Month 10 ^a	Month 11 ^a	EOT Month 12	EOS up to Month 13
	(V1)	(V2)	(V3)	(V4)	(V5)	(V6)	(V7)	(V8)	(V9)	(V10)	(V11)	(V12)	(V13)	(V14)
Visit Window	Day 1	(±3)	(±3)	(±3)	(±3)	(±3)	(±3)	(±3)	(±3)	(±3)	(±3)	(±3)	(±3)	(±3)
Informed Consent ^b	X	–	–	–	–	–	–	–	–	–	–	–	–	–
Medical History ^c	X	–	–	–	–	–	–	–	–	–	–	–	–	–
Pregnancy test ^d	X	X	X	X	X	X	X	X	X	X	X	X	X	–
SGRQ (Part I and II)	X	–	–	–	–	–	X	–	–	–	–	–	X	X
EQ-5D-3L	X	–	–	–	–	–	X	–	–	–	–	–	X	X
Physical examination	X	X	–	X	–	–	X	–	–	X	–	–	X	X
Body weight	X	X	–	X	–	–	X	–	–	X	–	–	X	X
Vital signs and pulse oximetry ^e	X	X	X	X	X	X	X	X	X	X	X	X	X	X
6 minute walk test	X	–	–	–	–	–	X	–	–	–	–	–	X	–
Audiology test	X ^f	–	–	–	–	–	X	–	–	–	–	–	X	–
Concomitant medications ^g	X	X	X	X	X	X	X	X	X	X	X	X	X	X
Healthcare Resource Utilization	X	X	–	X	–	–	X	–	–	X	–	–	X	–
AE assessment ^h	X	X	X	X	X	X	X	X	X	X	X	X	X	X
Sputum collection for microbiology	X	X	X	X	X	X	X	X	X	X	X	X	X	–

INS-312	TREATMENT PHASE													OFF-ALIS TREATMENT PHASE
	Baseline	Month 1	Month 2 ^a	Month 3	Month 4 ^a	Month 5 ^a	Month 6	Month 7 ^a	Month 8 ^a	Month 9	Month 10 ^a	Month 11 ^a	EOT Month 12	EOS up to Month 13
	(V1)	(V2)	(V3)	(V4)	(V5)	(V6)	(V7)	(V8)	(V9)	(V10)	(V11)	(V12)	(V13)	(V14)
Visit Window	Day 1	(±3)	(±3)	(±3)	(±3)	(±3)	(±3)	(±3)	(±3)	(±3)	(±3)	(±3)	(±3)	(±3)
Chemistry	X	X	–	X	–	–	X	–	–	X	–	–	X	–
Hematology	X	X	–	X	–	–	X	–	–	X	–	–	X	–
Urinalysis	X	X	–	X	–	–	X	–	–	X	–	–	X	–
Serum for biomarkers (CRP and IL-6)	X	–	–	–	–	–	X	–	–	–	–	–	X	–
Sub-Study: CT scan of chest ⁱ	X	–	–	–	–	–	–	–	–	–	–	–	X	–
Sub-Study: CT scan of chest ⁱ (Japan)	X	–	–	–	–	–	X	–	–	–	–	–	X	–
Send sputum collection containers home	X	X	X	X	X	X	X	X	X	X	X	X	–	–
Administer study drug at site	X	X	X	X	X	X	X	X	X	X	X	X	–	–
Dispense study drug ^k	X	X	X	X	X	X	X	X	X	X	X	X	–	–
Collection of study drug vials	–	X	X	X	X	X	X	X	X	X	X	X	X	–

^a Home Healthcare visits may be available for sites with IRB/EC approval to conduct Home Healthcare visits, and for qualifying subjects who may have difficulty attending clinic visits.

^b Subjects will be asked to provide written informed consent at their INS-212 EOT visit.

^c All ongoing medical history conditions from INS-212 must be listed within the medical history eCRF for INS-312. Any chronic conditions that require medication must be listed in the medical history eCRF.

^d Urine pregnancy testing will be performed on all women of child bearing potential. Women not of child bearing potential are defined as postmenopausal (i.e., amenorrheic for at least 1 year), or surgically or naturally sterile.

^e At visits where study drug is administered, vital signs and pulse oximetry will be performed before and after study drug administration.

^f The Baseline audiology examination must be performed on Day 1 before the administration of study drug.

^g All ongoing medication(s) from the INS-212 study must be documented in the concomitant medication eCRF for INS-312; this includes any ongoing medication(s) that were recorded in INS-212 prior to the first dosing in INS-312.

[figure not shown]
^h All ongoing AEs from the INS-212 study will be documented as medical history for INS-312. At visits where study drug is administered, AEs will be assessed before and after administration of study drug. Any AE that has occurred and resolved before administration of the study drug on Day 1 (Baseline) will be documented for study INS-212.

ⁱ Only for subjects who agreed to participate in the CT Scan sub-study in INS-312. Subjects will have a chest CT scan at Baseline (Day 1), if not already done at the INS-212 EOT Visit. Subjects will have a follow-up chest CT scan at the EOT visit, provided the last chest CT scan was not obtained within the prior 6 months. High resolution CT scan is preferred, if available. Please refer to APPENDIX 3 for additional details on the CT Scan sub-study.

^j Only for subjects in Japan. Subjects will have a chest CT scan at Baseline (Day 1), if not already done at the INS-212 Month 6 visit. Subjects will also have chest CT scans at Month 6 and at the EOT visit, provided the last chest CT scan was not obtained within the prior 6 months. High resolution CT scan is preferred, if available. Please refer to APPENDIX 4 for additional details on the Japan specific CT Scan sub-study.

^k Study drug will be dispensed to all subjects up to and including the Month 11 visit.

